## **10 STATISTICAL CONSIDERATIONS**

### **10.1 Sample Size Determination**

#### **10.1.1 Dose Escalation**

##### **10.1.1.1 Monotherapy Dose Escalation (Part 1)**

Dose escalation during the BMS-986277 monotherapy dose escalation (Part 1) will be guided by BLRM employing the Escalation With Overdose Control (EWOC) principle. The BLRM method is fully adaptive, makes use of all the information available at the time of each dose assignment, not just data from the current dose level, and directly addresses the ethical need to control the probability of overdosing. Furthermore, the BLRM uses the knowledge gained from participants treated with enadenotucirev. The targeted toxicity rate in this study is in the range of [16%, 33%]. The boundary is similar to the toxicity boundary used by a rule-based design (ie, 3 + 3 design) in that a minimum is set to 16% (approximately 1 in 6) DLT rate and a maximum at 33% (approximately 2 in 6) DLT rate. The use of the EWOC principle limits the risk of exposing participants in the next cohort to an intolerable dose by ensuring the posterior probability of the DLT rate exceeding 33% at any dose is capped at 35%.

Due to the nature of the dose escalation process, the exact number of participants to be treated at each dose level cannot be precisely determined. The maximum number of participants to be treated is approximately 24. However, simulation studies with various scenarios show that the expected number of DLT-evaluable participants is no more than approximately 18 ([Appendix 9](#)). Additional participants (up to a total of 12) may be treated at any dose level to further evaluate the safety, PK, and/or pharmacodynamics profile. The total sample size is up to 72.

Approximately 3 participants will be treated at the starting dose levels of BMS-986277. While the BLRM will use DLT information from the DLT period only, clinical assessment will take into consideration the totality of available data, including PK/pharmacodynamics from all treated participants in assigning a dose level for the next cohort of 3 participants. At least 6 DLT-evaluable participants will be treated at a dose level before it can be recommended as the BLRM-RD for BMS-986277 monotherapy.

The BLRM-RD for BMS-986277 monotherapy is the dose that satisfies the following 3 conditions:

- 1) The empirical posterior probability that the “DLT rate of 16% to < 33%” is greater than a pre-specified value (ie, 50%);

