## 2 DOSE ESCALATION PROCESS AND SIMULATIONS IN MONOTHERAPY

### 2.1 Dose Escalation Process

Dose escalation recommendations for BMS-986277 monotherapy will be based on the inference from the Bayesian posterior and the probability that the true DLT rate for each dose lies in 1 of the following categories:

- [0%, 16%) under-dosing
- [16%, 33%) targeted toxicity
- [33%, 100%] excessive toxicity

Note: “[” or “[” is inclusive of the respective endpoint, and “(” or “)” exclusive of the respective endpoint.

These boundaries are similar to the toxicity boundaries used by a rule-based design (ie, 3 + 3 design) in that a minimum is set at 16% (~ 1 in 6) DLT rate and a maximum at 33% (~ 2 in 6) DLT

rate. Following the principle of EWOC, dose recommendations for the next cohort will be based on the Bayesian model after DLT information becomes available during the DLT period, accounting for all of the available data from the administered doses, and the candidate doses for the next cohort are the ones fulfilling the overdose criterion that there is no greater than 35% chance of excessive toxicity. Only the candidate doses will be considered for the next cohort. While the Bayesian model will use DLT information from the DLT period only, clinical assessment will take into consideration the totality of available data including PK/pharmacodynamics from all treated participants.

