### Interpretation and Use of [Figure 2](#):

[figure not shown]
Figure 2 is a snapshot of stacking histogram with DLT information available at dose level  $3 \times 10^{10}$  vp and  $3 \times 10^{11}$  vp. This figure will be updated each time new DLT information becomes available.

When recommending the next dose level, the model will first exclude doses that are intolerable (with overdosing probabilities > 35%, the rate that has been specified for BMS-986277). Among those qualified candidate doses that are considered “tolerable”, the model will select the dose that maximizes the probability of being within the target toxicity range (DLT rate between 16% and 33%). However, there will be no dose skipping during the dose escalation monotherapy phase of the study.

As illustrated in Figure 2, the distribution of predicted DLT rates will be characterized into possibilities falling into 3 different categories. First, dose levels  $3 \times 10^{12}$  vp for BMS-986277 are excluded according to the higher-than-cutoff overdosing probabilities (0.579 for  $3 \times 10^{12}$  vp). Among the remainder of tolerable dose levels, the BLRM recommends the dose that maximizes the probability of being within the target dosing interval. Therefore, the model’s recommendation would be to stay at  $1 \times 10^{12}$  vp, which is associated with the highest target dosing probability of 0.418 compared with that of  $3 \times 10^{10}$  vp (0.068) and  $3 \times 10^{11}$  vp (0.254).

Similarly (although not shown on Figure 2), according to the rules specified above, the model could possibly recommend to de-escalate to a lower dose level than the current treated dose level, escalate to the next dose level, or even recommend to stop and identify a new dose level lower than  $3 \times 10^{10}$  vp, the lowest pre-specified dose level. Please refer to the description of [Figure 1](#) for details on how to specify the new dose levels.

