**3.1 Example of using the BLRM for BMS-986277 Monotherapy Dose Escalation**

[figure not shown]
According to safety consideration and clinical judgement, the dose level  $3 \times 10^{10}$  vp is recommended as the starting dose for BMS-986277 monotherapy. With the current BMS-986277 prior specified in the Section 1.2 and all available DLT information up to  $3 \times 10^{12}$  vp, a

corresponding decision tree illustrating various models' recommendations under all possible scenarios for the first two cohorts is provided in Figure 4.

Tracing a branch of the decision tree in Figure 4 illustrates the decision making process. Taking the left-most branch of the tree as an example, starting at  $3 \times 10^{10}$  vp, if there were 0 DLTs observed in the real clinical trial, the model would recommend to escalate to  $3 \times 10^{11}$  vp (the BLRM actually recommends escalating to the highest dose  $3 \times 10^{12}$  vp, but since this is a 100-fold increase of dose and dose skipping is not allowed, the dose level  $3 \times 10^{11}$  vp is selected), one level above the current treated dose level according to the escalation rules per protocol. Next, if there is 0 DLTs observed at  $3 \times 10^{11}$  vp, the model would recommend to escalate further to  $1 \times 10^{12}$  vp. At  $1 \times 10^{12}$  vp, there would be 3 potential decisions (0/3 escalate, 1/3 and 2/3 would stay, and 3/3 would de-escalate); this is not shown due to crowding the diagram.

During the actual clinical study, the tree would be narrowed or deepened based on actual DLTs observed. The clinical team will be able to leverage this decision tree to preview decisions at each interim monitoring step and to plan proactively.

**Figure 4: The BLRM Model Hypothetical Decision Tree for BMS-986277 Monotherapy during Dose Escalation (for the first 2 cohorts)**

Abbreviations: DE = de-escalation; E = escalation; S = stay.

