#### 1 INTRODUCTION AND DOCUMENT HISTORY

This statistical analysis plan (SAP) supersedes the statistical considerations identified in the protocol; where considerations are substantially different, they will be identified as such in this document. In the event that the protocol has amendment(s) that do not have an impact on the statistical analysis methodology, this SAP will not require an amendment. If additional analyses are required to supplement the planned analyses described in this SAP, they may be performed and will be identified in the Clinical Study Report (CSR).

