# 6.1 Monotherapy Dose Escalation (Part 1)

Dose escalation during the BMS-986277 monotherapy dose escalation (Part 1) will be guided by BLRM employing the Escalation with Overdose Control (EWOC) principle. The BLRM method is fully adaptive, makes use of all the information available at the time of each dose assignment, not just data from the current dose level, and directly addresses the ethical need to control the probability of overdosing. Furthermore, the BLRM uses the knowledge gained from participants treated with enadenotucirev, because BMS-986277 is the genetically modified form of enadenotucirev. The targeted toxicity rate in this study is in the range of [16%, 33%). The boundary is similar to the toxicity boundary used by a rule-based design (ie, 3 + 3 design) in that a minimum is set to 16% (approximately 1 in 6) DLT rate and a maximum at 33% (approximately 2 in 6) DLT rate. The use of the EWOC principle limits the risk of exposing participants in the next cohort to an intolerable dose by ensuring the posterior probability of the DLT rate exceeding 33% at any dose is capped at 25%.

Due to the nature of the dose escalation process, the exact number of participants to be treated at each dose level cannot be precisely determined. The maximum number of participants to be treated is approximately 24. However, simulation studies with various scenarios show that the expected number of DLT evaluable participants is no more than approximately 18 (Protocol Appendix 9).

Approximately 3 participants will be treated at the starting dose levels of BMS-986277. While the BLRM will use DLT information from the DLT period only, clinical assessment will take into consideration the totality of available data, including PK/pharmacodynamics from all treated participants in assigning a dose level for the next cohort of 3 participants. At least 6 DLT-evaluable participants will be treated at a dose level before it can be recommended as the BLRM-recommended dose (BLRM-RD) for BMS-986277 monotherapy.

The BLRM-RD for BMS-986277 monotherapy is the dose that satisfies the following 3 conditions:

- 1) The empirical posterior probability that the "DLT rate of 16% to < 33%" is greater than a prespecified value (ie, 50%);
- 2) This probability needs to be the largest among the dose levels that satisfy the EWOC condition (ie, the probability that the "DLT rate  $\geq$  33%" must be no greater than 35%);

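### SAP 6.1 caps the overdose probability for the next cohort at 25%, but its own BLRM-RD condition and every Part 1 rule in the protocol use 35%

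*SAP*

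**What the plan says.** SAP 6.1, opening paragraph, on which doses the next cohort may receive: "ensuring the posterior probability of the DLT rate exceeding 33% at any dose is capped at 25"%.

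SAP 6.1, BLRM-RD condition 2, which names the EWOC condition: the probability that the DLT rate is at least 33% "must be no greater than 35"%.

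Protocol 10.1.1.1, the matching sentence: "ensuring the posterior probability of the DLT rate exceeding 33% at any dose is capped at 35"%.

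Protocol Appendix 9, section 2.1, on candidate doses for the next cohort: "overdose criterion that there is no greater than 35% chance of excessive toxicity".

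Protocol Appendix 9, interpretation of Figure 2: doses are excluded "with overdosing probabilities > 35%, the rate that has been specified for BMS-986277".

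Appendix 9 also uses 35% in its BLRM-RD definition, in the simulation settings of section 2.2 and in the interpretation of Figure 1. The combination rules in its section 5 use 35% as well.

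SAP section 1 says the SAP supersedes the protocol's statistical considerations and that "where considerations are substantially different, they will be identified as such in this document". Neither SAP 6.1, the revision history nor the amendment table mentions a change to the cap.

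**The concern.** The cap determines which doses may be given to the next cohort, so it is the main safeguard against overdosing in Part 1. The SAP gives it two values in one section. Reading them as two separate rules, 25% for the next cohort and 35% for the final recommendation, does not work: Appendix 9 section 2.1 applies 35% to the next cohort, and condition 2 treats EWOC as a single condition.

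Because the SAP claims precedence, a reader cannot simply fall back on the protocol. SAP 6.1 also takes its expected size of about 18 DLT-evaluable participants from the Appendix 9 simulations, which were run with a 35% cap. If 25% applied, those operating characteristics would not describe the design.

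**Working it through.** **Which value fits the text.** Setting the statements side by side, 25% appears once, in SAP 6.1. All the others listed above say 35%, including one in SAP 6.1 itself.

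**Whether the difference changes a decision.**

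Inputs, from protocol Appendix 9:
- Model: two-parameter BLRM, logit(p) = log(α) + β·log(dose / 3×10^12).
- Prior for (log α, log β), Table 2 and section 2.2: means (−0.959, 0.884), SDs (1.005, 1.240), correlation 0.055, bivariate normal.
- Intervals: below 16%, 16% to below 33%, and 33% or more.
- Doses: 3×10^10, 3×10^11, 1×10^12 and 3×10^12 vp.

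Method: the posterior is proportional to the prior times the product over doses of p^y(1−p)^(n−y). It was integrated numerically on a fine grid with cell edges aligned to logit(0.33).

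*Step 1. Reproduce the Figure 2 example (0/3 at 3×10^10, 1/3 at 3×10^11).*

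| Quantity | Protocol | Recomputed |
|---|---|---|
| P(target) at 3×10^10 | 0.068 | 0.068 |
| P(target) at 3×10^11 | 0.254 | 0.257 |
| P(target) at 1×10^12 | 0.418 | 0.415 |
| P(overdose) at 3×10^12 | 0.579 | 0.561 |

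The largest gap is 0.579 − 0.561 = 0.018.

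*Step 2. Check the decision branches at 1×10^12 after 0/3 and 0/3.* Appendix 9 section 3.1 says "there would be 3 potential decisions (0/3 escalate, 1/3 and 2/3 would stay, and 3/3 would de-escalate".

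| Result at 1×10^12 | Deciding P(overdose) | Decision at 35% | Decision at 25% |
|---|---|---|---|
| 0/3 | 0.349 at 3×10^12 | escalate | stay |
| 1/3 | 0.063 at 1×10^12 | stay | stay |
| 2/3 | 0.236 at 1×10^12 | stay | stay |
| 3/3 | 0.504 at 1×10^12 | de-escalate | de-escalate |

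The 35% column matches the protocol in all four rows. The 25% column fails in the first.

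*Step 3. Continue without DLTs.* P(overdose) at 3×10^12 after 0/3, 0/3 and then 0/n at 1×10^12 is 0.349 for n = 3, 0.331 for n = 9 and 0.328 for n = 12. Twelve is the maximum per dose, so under 25% a trial with no DLTs at the first three doses could not open 3×10^12.

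The top dose is not unreachable at 25%. An early DLT flattens the fitted curve, so 0/3, 1/6, 0/9 gives 0.223 and 0/3, 1/6, 0/12 gives 0.183.

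*Step 4. Simulate, for direction only.* The run used 10,000 trials per scenario and cap, cohorts of 3, no dose skipping, and at most 12 per dose and 24 in total.

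| Scenario | Selects 3×10^12: Table 3 | Selects 3×10^12: this run, 35% | Reaches 3×10^12: 35% | Reaches 3×10^12: 25% |
|---|---|---|---|---|
| By prior | 49.3% | 25% | 92% | 0% |
| Flatter | 32.3% | 26% | 56% | 10% |
| Narrow window | 14.2% | 4% | 86% | 4% |
| All low | 89.0% | 70% | 100% | 0% |
| All within | 10.7% | 10% | 24% | 5% |

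Table 3 was not reproduced; the sponsor's runs allowed dose skipping. The 35% results also depend on the grid: a coarser one gave 0.355 instead of 0.349 at the critical step, and a 2,000-trial run on it reached the top dose in 81.5% of trials in the by-prior scenario. The 25% results barely moved.

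**The case against.** Four points deserve an answer.

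- **Version gap.** SAP version 1.0 incorporates changes up to Revised Protocol 03, while the protocol supplied is Revised Protocol 06. Revised Protocol 03 updated Appendix 9 and Revised Protocol 05 updated the statistical considerations, so the 25% may once have matched the protocol. This stands as far as the cause goes: the documents do not show whether 25% is leftover text, a typing error or an intended change. It does not touch the conflict inside SAP 6.1.
- **Practical effect.** Escalation is run from the protocol, which consistently uses 35%. The SAP serves the study report, and no analysis in its section 8 uses the cap. The stray value is also the stricter one, so following it would not expose participants to more toxicity. This limits the harm, but the SAP still says it supersedes the protocol's statistical considerations.
- **Near tie.** Passing 35% at 0.349 is a margin of 0.001, smaller than the 0.018 gap in the Figure 2 check. The calculation cannot prove that branch by itself; the protocol's text does. Failing 25% is much clearer, since the smallest no-DLT value, 0.328, is 0.078 above it.
- **Imperfect replication.** Appendix 9 section 3.1 says the model would recommend 3×10^12 straight after 0/3 at the lowest dose. The recalculation gives an overdose probability of about 0.39 there, which exceeds 35%. Together with the mismatch to Table 3, this means the simulated percentages should be read for direction only.

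**Conclusion.** The concern holds. SAP 6.1 states one decision threshold as both 25% and 35%, the protocol supplied supports only 35%, and the SAP does not identify the difference. Whether 25% departed from Revised Protocol 03 cannot be determined.

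The discrepancy has consequences: a literal 25% cap reverses the protocol's 0/3 escalation branch at 1×10^12 vp and closes the top dose on every path without DLTs. That result rests on the Table 2 mixture row used as a single bivariate normal prior. Using the two mixture components separately also gives 0.349 after three 0/3 cohorts, and 0.346 to 0.347 for 0/6 to 0/12 at 1×10^12 vp, so failure at 25% does not depend on that choice.

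This should be fixed, but the consistent protocol rules keep the operational risk low. The textual contradiction does not depend on any of the calculations.

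**What to change.** Change 25% to 35% in the opening paragraph of SAP 6.1. The cost is one number in one sentence. Table 3 and the decision tree need no rerun, because they already use 35%.

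If 25% is truly intended, the work is larger. The SAP must identify it as a change and align BLRM-RD condition 2. Protocol 10.1.1.1 and Appendix 9 must be amended, and Table 3 and the decision tree rerun at 25% before the next escalation decision.

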# 6.2 Combination Dose Escalation (Part 2)

The dose level for BMS-986277 in combination with nivolumab will be determined based on the RD for BMS-986277 monotherapy established in Part 1, the BLRM-copula recommended dose with nivolumab monotherapy, and incorporating knowledge gained from participants treated with enadenotucirev in combination with PD-1 inhibitor (nivolumab or pembrolizumab). The starting dose for BMS-986277 in combination with nivolumab will be 1 dose level below the RD.

Initially, approximately 3 participants will be treated at this dose level and escalation will be guided by BLRM-copula. While the BLRM-copula will use DLT information from the DLT period only, clinical assessment will take into consideration the totality of available data, including PK/pharmacodynamics from all treated participants in assigning a dose level for the next cohort of 3 participants. At least 6 DLT-evaluable participants will be treated at a dose level before it can be recommended as the BLRM-copula recommended dose for BMS-986277 in combination with nivolumab. Additional participants (up to a total of 15) may be treated at any dose combination below or at the BLRM-copula recommended dose for further evaluation of safety, PK, or pharmacodynamic parameters as required. A combination with a lower, intermediate, or higher dose level of BMS-986277 may be considered if the BLRM-copula recommends it, after consideration of all available safety, PK, and pharmacodynamic data.

The final recommended Phase 2 dose (RP2D) for BMS-986277 in combination with nivolumab will be based on the recommendations from the BLRM-copula and overall clinical assessment of all available safety, PK, pharmacodynamic, and efficacy data. This final RP2D will be used in the cohort expansion.

# 6.3 Cohort Expansion (Part 3)

Sample size calculations for cohort expansion assumes the following:

- Assumes response rates below 6% and 20% for the low CD8 and mid CD8 cohorts, respectively, would not warrant further study. These are the approximate response rates in CA209275 participants with CD8 < 2% and  $2\% \le CD8 < 20\%$ , respectively.
  - These cutoffs are based on CD8 IHC data from CA209275, a nivolumab-only clinical study in participants with UC for which response by BIRC data is available.
- Assumes 2 or more indications per cohort
- Assumes the treatment effect is the same across indications within a cohort
- The nominal error rates are controlled at one-sided  $\alpha$ =0.10 and  $\beta$ =0.20, but the actual power and type I error are shown in the tables below (Table 4 and Table 5), which accounts for the discrete nature of the binomial distribution.

# 6.3.1 Cohort 1 (CD8 < 2%)

Assuming a 6% response rate for nivolumab monotherapy, the interesting rate for the combination therapy is 20%, then 35 participants are needed to detect at least 14.3% response rate.

Table 4: Power Estimates and Type I Error for Cohort 1

		Historical Rate			
	X, N (alpha, power)	0.05	0.06		
get ite	0.15	6, 55 (0.056, 0.852)	8, 72 (0.066, 0.864)		
Target Rate	0.20	4, 28 (0.049, 0.840)	5, 35 (0.056, 0.857)		
X is the min # of responders to show not futile					

# 6.3.2 Cohort 2 (2% <= CD8 < 20%)

Assuming a 20% response rate for nivolumab monotherapy, the interesting rate for the combination therapy is 40%, then 33 participants are needed to detect at least a 33% response rate.

Table 5: Power Estimates and Type I Error for Cohort 2

		Historical Rate		
	X, N (alpha, power)	0.15	0.20	
Target Rate	0.30	12, 49 (0.055, 0.841)	31, 121 (0.079, 0.876)	
	0.35	8, 29 (0.059, 0.849)	16, 57 (0.091, 0.893)	
	0.40	6, 19 (0.054, 0.837)	11, 33 (0.051, 0.831)	
X is the min # of responders to show not futile				

# 7 STUDY PERIODS, TREATMENT REGIMENS AND POPULATIONS FOR ANALYSES

# 7.1 Study Periods

## 7.1.1 Baseline Period

Baseline evaluations or events will be defined as evaluations or events that occur before the date and time of the first dose of study treatment, for all treated population, unless otherwise specified.

In cases where the time (onset time of event or evaluation time and dosing time) is missing or not collected, the following definitions will apply:

- Pre-treatment AEs will be defined as AEs with an onset date prior to but not including the day of the first dose of study treatment
- Baseline evaluations (laboratory tests, pulse oximetry and vital signs) will be defined as evaluations with a date on or prior to the day of first dose of study treatment
- Baseline CD8 value is value recorded closest to (before or on) the first treatment date and no earlier than 35 days prior to first dose. If multiple records at same date then select the highest value.

If there are multiple valid assessments at baseline, then the assessment that is closest to the date (and time if collected) of the first dose of study treatment will be used as the baseline in the analyses. If multiple assessments are collected at the same date (and time if collected), the assessment with the latest database entry date (and time if collected) will be considered as baseline.

#### 7.1.2 Post-Baseline Period

- On-treatment period for evaluation of AEs and measurements (including laboratory tests) post baseline is defined as on or after the first dose of study treatment up to and including 30 days or 100 days after the last dose of study treatment for participants who are off study treatment, for Part 1 and Parts 2-3, respectively. For participants who are still on study treatment, the entire post-baseline period will be counted as on-treatment.
- Primary analysis of safety endpoints will be based on the treatment period.
- DLTs will be evaluated during the 42-day DLT period.

